The Apos Device. (a) Biomechanical device comprising two individually calibrated elements and a foot-worn platform. The elements are attached to a platform under the hindfoot and forefoot regions. (b) The biomechanical elements are available in different degrees of convexity and resilience. (c) The specially designed sole of the platform includes two mounting rails and a positioning matrix to enable flexible positioning of each biomechanical element. [Elbaz, 2014].

Figure 2. The sham device

CONFIDENTIAL

This material is the property of the NYU School of Medicine and Langone Medical Center. Do not disclose or use except as authorized in writing by the study sponsor

Objectives and Hypothesis of Study

1. The primary objective is to evaluate the efficacy of AposTherapy® at 6 months, with the primary efficacy assessment based on improvement in knee pain score and improvement in function in patients with knee OA. The hypothesis is that patients fitted with the calibrated AposTherapy® device will demonstrate an improvement in knee pain intensity and improvement in function compared to patients who are fitted with a sham-placebo Apos device.
2. After completion of 6 months of therapy, patients will be un-blinded to their group allocation and the second phase of the study will commence, including the following aims:
 - a. To evaluate the long-term (12 months) effect of AposTherapy® on the level of pain and the level of function of patients with knee OA. We hypothesize that patients will maintain the diminished levels of pain and improved function.
 - b. To evaluate the changes in the level of pain and the level of function of patients that were originally allocated to the control group and will now cross-over and commence AposTherapy® treatment for 6 months. We hypothesize that patient will report an improvement in the level of pain and improvement in function following 6 months of treatment.

Primary Efficacy Endpoints

- Phase I:
 - Improvement in knee pain score and improvement in function, as measured by change from baseline Western Ontario and McMaster University (WOMAC) score to 6 months post treatment.
- Phase II:
 - Long-term effect (12 months) of AposTherapy on pain and function, as measures by WOMAC, of patients with knee OA
 - Improvement in knee pain and knee function, as measured by WOMAC, of patients with knee OA that were allocated to the sham control group and have crossed-over to the active group, receiving AposTherapy for 6 months.

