- Patients who have had a joint replacement or other major surgery to the knee, hip or ankle (ipsilateral or contralateral side).
- Patients suffering from neuropathic arthropathy.
- Patients with an increased tendency to fall.
- Patients exhibiting a lack of physical or mental ability to perform or comply with the study procedure.
- Patients with a history of pathological osteoporotic fracture.
- Patients suffering from symptomatic degenerative arthritis in lower limb joints other than the knees.
- Patients with referred pain in the knees from primary back or hip joint pain.
- Patients with neurological deficits to the lower extremity (ex. foot drop)
- Patients whose shoe size is less than US 4 and greater than US 12
- Patients who have had arthroscopy within 6 months of the study
- Patients with inflammatory arthropathy
- Patients with any central nerve system disease/neurological problem (i.e. Parkinson's, post CVA (stroke), etc.).

Vulnerable Subjects

We do not intend to enroll vulnerable subjects.

Subject Withdrawal

Patients are free to withdraw at any time from the study. While participating in the study, patients should avoid any other treatment modality apart from rescue pain medication (Acetaminophen/Paracetamol) as long as it is possible. If patients require injection therapy or surgery on the study knee(s) during the course of the study, the patient will be withdrawn from further data collection.

III. METHODS AND PROCEDURES

Sample Size Analysis

Assuming normality on the data, we calculated the statistical power for various detectable effect sizes listed in Table X using PASS 2011 software (http://www.ncss.com/download_PASS11.html). The analysis of power is performed conservatively by assuming the largest variability in pain scores observed in the preliminary data (e.g., reduction of pain scores of 3.0 in active group and 0 of control group with a pooled standard deviation of 3.60 corresponds to an effect size of 0.8. After accounting for a 10% loss to follow-up we would expect to enroll 60 patients in each group for a total of 120 patients. With 120 samples (60 each), the two-sided t-test will have 80% power at the 0.05 significance level to detect differences of pain score of 0.8 SD units between control and case [Bar-Ziv, 2013].

Methods and Procedures

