Phase I - A prospective, interventional, randomized, double-arm clinical evaluation study. Patients over the age of 45 years who come into the office with symptomatic knee pain, and a Kellgren-Lawrence grade more than or equal to grade 2, and have pain levels above 2\10 may be included in the study.

Patient progress will be monitored for a six (6) months period, consisting of information from office visits and scores obtained at each study visit. Patients will be asked to return to the physician's office at specific time points (3 months and 6 months after the initial visit). After signing consent patients will be randomized to one of two groups:

- **Group 1: AposTherapy® Active Arm**
- **Group 2: AposTherapy® Control Arm**

Randomization Process

Blocked randomization will be used to assign subjects to their respective treatment arms. The allocation ratio will be one to one and the random method of selection will be through a computerized random

CONFIDENTIAL

This material is the property of the NYU School of Medicine and Langone Medical Center. Do not disclose or use except as authorized in writing by the study sponsor

number generator. The on-site coordinator will be responsible for entering and maintaining the subject randomization information. After randomization has been completed, research personnel will review and document the patient's demographics, medical, and surgical history on the study case report forms. The baseline patient-reported outcome questionnaires will then be completed (these include the WOMAC, VAS, SF-36). The physician and research team will then perform a clinical evaluation of the knee.

Active Arm Process

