This material is the property of the NYU School of Medicine and Langone Medical Center. Do not disclose or use except as authorized in writing by the study sponsor

Data Analysis

Phase I:

- Primary outcome measures will include comparing scores at baseline and the following study time points (baseline, 3 months and 6 months) obtained from the WOMAC. The WOMAC is a validated outcomes assessment used to measure patients' opinion about their knee and associated problems.
- Secondary outcome measures will include comparisons of all measured variables between baseline and all time points including VAS score, SF-36 score, improvement and maintenance in knee function using physical examination findings (these include, but are not limited to: Pain, Knee Effusion, Ligament Stability, Stability, Strength, Range of Motion, Sensation, Posture/alignment); and monitoring usage of rescue medications or NSAIDs. All data will be obtained from the completed case report forms that are being utilized for this study.

Phase II:

- Original active group – evaluating the changes in pain, function, quality of life and usage of rescue medications or NSAIDs following 12 months of therapy.
- Cross-over group – comparing scores at baseline and the following study time points (baseline, 3 months and 6 months) obtained from the WOMAC, SF-36, knee function and usage of rescue medications or NSAIDs.

DATA SAFETY MONITORING PLAN (DSMP)

I. Study Monitoring

The principal investigator, [name], will be the data safety monitor for this project. After a three (3) months follow-up period, [name] will review the data for SAE's, protocol deviations and other issues. If it is determined that certain events occur above an expected rate (i.e. increased knee pain), then enrollment will be stopped.

II. Types of Data

Under this DSMP, the following data/events will be captured and documented:

- Duration of AposTherapy® use;
- Monitoring of patient falls;
- Patient Outcomes Assessments;
- Reportable and/or adverse events
- Protocol Deviations

III. Responsibilities and roles for gathering, evaluating and monitoring the data:

Principal Investigator

After a three (3) months follow-up period, the PI will meet with any co-investigators and the Research Coordinator to discuss the current findings and analysis. During these meetings, the PI will also be responsible for verifying data accuracy, and compliance with the study protocol.

Research Coordinator

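### The only test named is an unadjusted t-test and no baseline covariate is planned; if WOMAC change is analysed that way, the treatment-effect variance is larger than it need be

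*Combined protocol and SAP*

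**What the plan says.** - **Endpoint.** Primary Efficacy Endpoints defines the Phase I endpoint as improvement in pain and function, "as measured by change from baseline Western Ontario and McMaster University (WOMAC) score to 6 months post treatment".
- **Test.** The only inferential test appears in Sample Size Analysis, repeated under Statistical Methodology in the Study Summary: "the two-sided t-test will have 80% power at the 0.05 significance level to detect differences of pain score of 0.8 SD units". It refers to a pain score, and WOMAC is not mentioned there.
- **Analysis.** Data Analysis, Phase I, says "Primary outcome measures will include comparing scores at baseline and the following study time points" and lists baseline, 3 months and 6 months for the WOMAC. It names no test, model or covariate.
- **Planning inputs.** The assumed difference is 3.0 points, with no change in the control arm. On variability, the text says "pooled standard deviation of 3.60 corresponds to an effect size of 0.8". Enrolment is set at 60 per arm, 120 in all, which is said to allow for 10% dropout. The text does not say whether 3.60 is the SD of change or of a score at one visit. It gives no correlation between visits.
- **Baseline data.** Randomization Process, Phase I Study Visits and the Study schedule have every patient complete WOMAC, VAS and SF-36 at baseline. The first two list the questionnaires after the randomization step.
- **Allocation.** "The allocation ratio will be one to one", in blocks, with no stratification factor named.

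**The concern.** Put together, the stated endpoint and the only stated test give a two-sample t-test on change from baseline. Such a test subtracts the whole baseline score, which fixes the baseline slope at 1. When scores at the two visits have equal variance and correlation r, the slope that best predicts the month-6 score is r. Fixing it at 1 adds noise to the estimate. It also over-corrects any chance baseline difference between arms, by (1-r) times that difference: half of it at r = 0.5. With 60 per arm and no stratification, some chance imbalance in baseline WOMAC is to be expected.

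At stake are the width of the confidence interval for the primary comparison and its sensitivity to baseline imbalance. The data needed to improve both are already being collected.

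**Working it through.** **Inputs.** From Sample Size Analysis: difference 3.0 points, SD 3.60, two-sided alpha 0.05, 60 per arm, 10% loss, so 60 × 0.9 = 54 evaluable per arm. Assumed, because the documents are silent: r = 0.3, 0.5 or 0.7, and equal variances at baseline and month 6. Power is from the noncentral t.

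**1. The plan's own figure.** At 0.8 SD the t-test has 99.1% power with 60 per arm and 98.5% with 54. At 3.0/3.60 = 0.833 SD it has 99.5% and 99.0%. The stated 80% is not reproduced. That is a separate matter, but it shows that the planned case is far from short of power.

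**2. Variance of the two analyses**, with s² the variance of a score at one visit:
- t-test on change: proportional to 2(1-r)s²
- ANCOVA on baseline: proportional to (1-r²)s²
- ratio: (1-r²)/[2(1-r)] = (1+r)/2, so the reduction is (1-r)/2

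| r | Variance ratio | Variance reduction | SE reduction |
|---|---|---|---|
| 0.3 | 0.65 | 35% | 19% |
| 0.5 | 0.75 | 25% | 13% |
| 0.7 | 0.85 | 15% | 8% |

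Over a wider range, the variance reduction is 50% at r = 0 and 5% at r = 0.9.

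**3. Confidence interval, if 3.60 is the SD of change.** SE = 3.60 × √(2/54) = 0.693. The half-width is 1.983 × 0.693 = 1.37 points. Multiplying by √0.65, √0.75 and √0.85 gives 1.11, 1.19 and 1.27 points.

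**4. Power with 54 per arm, if 3.60 is the SD of change.**

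| Net difference | t-test on change | ANCOVA, r = 0.3 | r = 0.5 | r = 0.7 |
|---|---|---|---|---|
| 3.0 (planned) | 99.0% | above 99% | above 99% | above 99% |
| 2.0 (illustrative) | 82% | 94% | 91% | 87% |

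**5. The other reading: 3.60 is a single-visit SD.** The SD of change is then 3.60 × √[2(1-r)] = 4.26, 3.60 and 2.79. At the planned 3.0 points the change-score t-test has power of 95%, 99% and nearly 100%. So under either reading, for r from 0.3 to 0.7, power at the planned difference is about 95% or more before any adjustment.

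**The case against.** **The plan does not commit to this analysis.** A reader might infer that the protocol prescribes an unadjusted t-test on WOMAC change. It does not. The t-test belongs to the power calculation, for a pain score, and Data Analysis would equally admit a repeated-measures model. This objection stands, so the finding is conditional: the named test is unadjusted, and no other analysis is specified.

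**The size rests on assumptions.** This also stands. Neither r nor equality of variances is documented. Entry requires VAS pain of at least 3, which truncates baseline pain but not follow-up pain, so equal variances are doubtful for pain. If month-6 scores alone were compared, the saving from adjustment would be r² (9% to 49% for r from 0.3 to 0.7) instead of (1-r)/2.

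**Power is already ample.** A reader might infer that the trial is underpowered without adjustment. At the plan's own 3.0 points it is not. The 2.0-point case above is illustrative and is not a figure from the plan. However, the planned difference assumes no change at all in the sham arm, whose patients also receive a foot-worn device, daily wearing instructions and repeated visits. If they improve, the net difference shrinks and the power gain becomes real.

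**Which SD is 3.60?** The wording fits an SD of the reduction better. If the pain score is on the 0-10 entry scale, baseline values lie between 3 and 10, where an SD cannot exceed about 3.5. A baseline SD of 3.60 would then be impossible. For this reason the confidence-interval result uses the SD-of-change reading. The variance ratio does not depend on the choice.

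**The unadjusted test is valid.** This is correct. Under randomization a t-test on change is unbiased and keeps its type I error. Nothing here suggests a wrong answer, only a less precise one.

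**Conclusion.** The point holds as a free improvement. The documents name one test, unadjusted, and plan no use of the baseline scores as covariates. If WOMAC change is analysed with that test, the variance of the treatment-effect estimate is larger than necessary. ANCOVA would remove 15% to 35% of it for r between 0.7 and 0.3, given equal variances at the two visits. The benefit is a narrower interval and less sensitivity to chance baseline imbalance. The gain in power matters only if the net difference falls below the planned 3.0 points. The documents do not support calling this a validity error, a shortfall in planned power, or a firm commitment to the weaker analysis.

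**What to change.** In Data Analysis, Phase I, name the primary analysis: ANCOVA of month-6 WOMAC pain and of month-6 WOMAC function, each on treatment arm plus its own baseline score, reporting the adjusted active-minus-sham difference with its 95% CI. Use the same model for VAS and SF-36, each with its own baseline. Keep the unadjusted t-test on change as a sensitivity analysis.

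In Randomization Process and Phase I Study Visits, move the baseline questionnaires ahead of the randomization step, so that they are completed before the allocation is known or the device is fitted. The covariate is then a true baseline. A change score needs the same safeguard, so the reordering is worthwhile whichever analysis is chosen.

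The cost is a few sentences in the analysis section and a change in the order of steps at the baseline visit. No new data, visits or patients are needed. ANCOVA uses one extra degree of freedom, which is negligible with 54 per arm.

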Secondary Efficacy Endpoints

- Phase I:
 - Improvement in WOMAC scores between all study time points – pre-treatment and following 3 months and 6 months post-treatment;
 - Improvement in Visual Analog Score (VAS) score between all study time points;
 - Improvement in Short-Form 36 (SF-36) score between all study time points;
 - Reduction in usage of pain killers or NSAIDS
- Phase II:
 - Original Active group - Improvement in knee pain and knee function scores, as measured by change from baseline WOMAC score to 12 months post treatment;
 - Original Active group - Improvement in VAS score between baseline and 12 months post treatment;
 - Original Active group - Improvement in SF-36 score between baseline and 12 months post treatment;
 - Original Active group - Reduction in usage of pain killers or NSAIDS
 - Cross-over group - Improvement in WOMAC scores between all study time points – pre-treatment and following, 3 months and 6 months post-treatment;
 - Cross-over group - Improvement in Visual Analog Score (VAS) score between all study time points;
 - Cross-over group - Improvement in Short-Form 36 (SF-36) score between all study time points
 - Cross-over group - Reduction in usage of pain killers or NSAIDS

CONFIDENTIAL

This material is the property of the NYU School of Medicine and Langone Medical Center. Do not disclose or use except as authorized in writing by the study sponsor

Outcome Measure Evaluation Criteria

Western Ontario and Mac Master University (WOMAC) – the WOMAC is a self-administered osteoarthritis outcomes instrument designed to assess lower extremity pain and function in osteoarthritis of the knee or hip. The minimal clinically important difference (MCID) proportion is a 16.0% reduction in WOMAC [Hmamouch, 2014].

Visual Analog Score (VAS) Scale - the VAS is a validated pain scale that asks subjects to rate the amount of pain they are currently experiencing on a line up to 100mm (no pain is equal to 0mm and the worst imaginable pain is equal to 100mm). An improvement of 20 points from the baseline score is considered a statistically significant improvement at that visit [Gallagher, 2001].

Short-Form (36) Health Survey – the SF-36 is a patient reported survey of health that is designed to measure health status. The survey consists of eight (8) sections, where the lower the score the more disability and the higher the score the less disability [Maruish, 2009].

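### Randomisation comes before the baseline WOMAC, VAS, SF-36 and knee examination, so the primary endpoint's baseline is recorded after allocation

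*Combined protocol and SAP*

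**What the plan says.** Methods and Procedures, Phase I, places allocation directly after consent: "After signing consent patients will be randomized to one of two groups". The Randomization Process section then gives a sequence in explicit time words:

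- History: "After randomization has been completed, research personnel will review and document" demographics and medical and surgical history.
- Questionnaires: "The baseline patient-reported outcome questionnaires will then be completed (these include the WOMAC, VAS, SF-36").
- Examination: "The physician and research team will then perform a clinical evaluation of the knee".

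The Visit 1/2 (Screening/Baseline) list has consent, criteria review and randomisation first, with history, knee evaluation, X-ray and questionnaires below. Device calibration by allocation follows at the treatment center.

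These baselines feed outcomes. Primary Efficacy Endpoints, Phase I, defines pain and function "as measured by change from baseline Western Ontario and McMaster University (WOMAC) score to 6 months post treatment". Data Analysis, Phase I, lists among the secondary outcome measures "improvement and maintenance in knee function using physical examination findings", compared between baseline and later time points.

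**The concern.** A baseline value should be one that knowledge of the patient's own assignment could not have affected. Completing baseline before allocation guarantees this whatever blinding is in place. With the stated order, the protection depends on nobody who performs or oversees the baseline assessments knowing the arm, and the plan does not secure that:

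- Only patient blinding is described. Nothing says whether the physician or research team is blinded.
- The on-site coordinator holds the randomisation information, and the Research Coordinator collects and documents study data (Data Safety Monitoring Plan). The plan does not say whether these are different people.
- Active Arm Process has the research team join the device team's clinical evaluation at the baseline visit. Control Arm Process names only the device team. As written, research staff have an arm-specific role at that visit, and the research team also takes part in the baseline knee examination.

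There is a second consequence. The screening/baseline assessments may be spread over more than one session. A patient randomised at the first who does not return for the second would be allocated with no baseline WOMAC, and so with no change score.

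**Working it through.** The point concerns the order of procedures. The plan gives no figure to reproduce, so the check sets the sections side by side.

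**1. Order of steps**

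| Source | Order given | Weight |
|---|---|---|
| Methods and Procedures, Phase I; Randomization Process | consent → randomisation → history → WOMAC/VAS/SF-36 → knee evaluation | explicit time words |
| Visit 1/2 list | consent → criteria review → randomisation → history → knee evaluation → X-ray → questionnaires | list order only; knee evaluation and questionnaires are reversed relative to the narrative, so it is not a strict clock |
| Study schedule | randomisation and all baseline rows share the week -2 column | no order stated within the column |

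The conclusion rests on the first row. The second agrees that randomisation comes first and the third does not contradict it. No section provides an earlier WOMAC, SF-36 or knee examination that could serve as a baseline recorded before randomisation.

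**2. What is affected**

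- Questionnaires placed after randomisation: WOMAC, VAS, SF-36 = 3 of 3.
- Examination domains named in Data Analysis, Phase I, and listed below randomisation in Visit 1/2: pain, effusion, ligament stability, stability, strength, range of motion, sensation, posture/alignment = 8 of 8.

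**3. How a baseline shift reaches the endpoint**

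The plan treats a reduction in WOMAC as improvement. Let B and F be the mean baseline and follow-up scores, with A for active and C for control. The unadjusted difference in improvement is

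(B_A − F_A) − (B_C − F_C) = (B_A − B_C) − (F_A − F_C).

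If knowledge of the arm moves the recorded active baseline by δ and leaves follow-up unchanged, the estimate moves by exactly δ. The documents give nothing from which to estimate δ, so no value is assigned.

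**4. What limits the route**

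- The outcome criteria section says "the WOMAC is a self-administered osteoarthritis outcomes instrument".
- The objectives say "After completion of 6 months of therapy, patients will be un-blinded to their group allocation".
- The schedule has baseline at week -2 and device administration at week 0, a gap of 0 − (−2) = 2 weeks. The baselines are therefore after allocation but before treatment.

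For the WOMAC, staff knowledge of the arm would have to reach the patient. For the knee examination it would not, because staff make the assessment themselves.

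**5. A related point, for reconciliation only**

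The X-ray used to set the Kellgren-Lawrence grade and the only scheduled VAS are listed after randomisation, although criteria review is listed before it. Other sections describe recruits as already eligible, and the schedule prints Radiography above Randomization. Eligibility pain is on 0-10 and the outcome VAS on 0-100 mm, so the eligibility score may be a separate presenting score. The plan does not say which film or pain score the criteria review uses.

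**The case against.** The strongest counter-case accepts the order and disputes its importance.

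- **Schedule.** The Full Research Assessment (Physician) row, which probably covers the knee examination, is printed above Randomization. Reading row order as sequence would put the schedule in conflict with the narrative on the very assessment most at risk. This is a fair qualification, but row order within a single column is not a stated sequence, and the narrative's time words remain the only explicit statement.
- **Status of the examination.** Knee examination is absent from the Secondary Efficacy Endpoints list and appears as a secondary outcome measure only under Data Analysis. This is true, and it lowers the stakes for that outcome. The count of 8 domains measures scope, not bias.
- **Primary endpoint.** Self-administration, patient blinding and the device coming after baseline make bias in the WOMAC baseline indirect. This stands, and it is why no bias is claimed to have occurred.
- **The deeper gap is staff blinding.** Re-sequencing does nothing for follow-up assessments, where the same staff may examine patients. This also stands. But the baseline can be protected at almost no cost without first settling staff blinding.

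**Conclusion.** The concern holds. As the Randomization Process section is written, the baseline of the primary change-from-baseline endpoint and of the examination outcome is recorded after allocation: 3 of 3 questionnaires and 8 of 8 examination domains. The order of steps is clear from the text. The consequence is conditional on someone at the baseline assessment knowing the arm, and its size is unknown. The risk is limited for the self-administered WOMAC and more direct for the staff-performed examination. The plan should be changed because the safeguard is nearly free and the primary endpoint depends on this baseline; the text alone does not show that the results would be biased.

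**What to change.** - **Methods and Procedures, Phase I, and Randomization Process:** state that patients are randomised only once eligibility is confirmed and all baseline assessments are recorded. Move history, WOMAC, VAS, SF-36 and the knee evaluation ahead of allocation.
- **Visit 1/2 list:** move the randomisation item below the X-ray, knee evaluation and questionnaires and before device calibration. The treatment-plan item is printed within the questionnaire list, so state whether randomisation comes before or after it.
- **Study schedule:** move the Randomization row below the Primary and Secondary Variables rows, so that the printed order matches the text.
- **Eligibility:** state that criteria review uses a Kellgren-Lawrence grade and a pain score recorded before randomisation. An existing standard-practice film may serve.

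The cost is re-sequencing within a visit that may already run over more than one session. There is no extra procedure, and sample size, power and alpha are unchanged. Allocation becomes available slightly later in the same visit, or at its second session. The change also reduces the chance of allocating a patient who has no baseline score. Staff blinding at follow-up still needs its own statement.
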